8.0 Study Endpoints*

8.1 ENDPOINT 1: The primary objective is to determine feasibility and acceptability of STAMP+CBT. Specifically, we will evaluate patients' adherence to daily and weekly comprehensive symptom selfassessments within the STAMP+CBT app. We will calculate patients' overall adherence rate and 95% confidence interval. Defined using precision analysis, we will consider the intervention to be feasible if >70% of subjects complete >4 of the 6 pain-CBT modules and completes 50% of surveys by the end of 4 weeks (completion of the 4week intervention study period; completion of the 2-week post intervention period will be exploratory).^{40,41} The intervention will be considered **acceptable** if >80% of the acceptability items are rated 4 or higher/5; lower ratings will lead to app refinements. Other feasibility measures will assess time to accrual, participation rates, study retention and completion rates, and the number of patients who continue to review app content between weeks 5-6 (post-intervention period). Power calculation: With 10 patients, we will be able to estimate these proportions with margins of error (half of a 95% confidence interval) of approximately 18% or less assuming that the feasibility threshold of 70% is reached. This margin of error is small enough so that proportion estimates relevant to study feasibility will be

accurate and provide informative guidance for future, larger studies. Using **qualitative** framework analysis methods, we will explore barriers/facilitators, suggested changes to content, acceptability of intervention engagement, and whether app use continues after completion. Although power is not sufficient in this pilot, we will explore associations between levels of engagement and changes in pain severity/interference, opioid use, catastrophizing, sleep, mood, and pain self-efficacy.

8.2 COMPREHENSIVE ENDPOINT: The study team will use qualitative and quantitative results to determine the feasibility and acceptability of this pain CBT mobile health app for patients with cancer. This feasibility study will inform final modification to the application and study procedures in preparation for a future efficacy study of the STAMP+ CBT mobile health app.

9 Procedures Involved*

9.1 STUDY PROCEDURES:

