The content for the STAMP+CBT application can be reviewed and referenced in appendices D, F, Y, Z. Once app programming is completely finalized, patients in the Pilot Cohort will engage in the pilot study to evaluate app feasibility and acceptability.

- 9.2 Patients in the Pilot Cohort will pilot the application for 4 weeks (or 6 weeks if they request to review the content further, this will allow us to test the correct length of app use). The onboarding and monitoring protocol is available in Appendix S. In addition, the RA will contact participants after 4 weeks (end of intervention period), and 6 weeks (end of 2-week post-intervention period). The purpose of these contacts would be to schedule the end of intervention interview and confirm completion of survey assessments, as well as the final survey assessments at 6 weeks (end of 2-week post-intervention period).
- 9.3 Participants will fall into only one eligibility category:

Pilot Cohort = Patient pilot testing

Description	Components of Participation

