An RA will ask the patient to complete a baseline survey assessment after consenting, at the end of the 4-week intervention study period, and at the end of the 2-week post intervention period to assess key outcomes (pain severity/interference,⁴² QOL⁴³), potential mediators of intervention effects (catastrophizing⁴⁴, self-efficacy⁴⁵, perceived stress⁴⁶, anxiety/depression⁴⁷, sleep⁴⁸), acceptability,⁴⁹ and usability⁵⁰. The survey can be completed remotely though a link to a Partners Healthcare compliant electronic survey system (e.g. REDCap), over the phone with the RA, over Zoom with the RA,

in person with pen and paper or on a tablet. The Baseline survey will assess socio-demographics, barriers to pain management, pain severity, opioid use, pain and psychological symptoms, and quality of life, with metrics shown in Table 5. End of 4-week intervention period survey will largely replicate the baseline survey; additionally, patients will rate their satisfaction with STAMP+CBT using the 6-item Acceptability E-scale. Surveys will be used to assess pain and psychological symptom trajectory, medication use, and quality of life. See **Appendix P** for the Baseline survey items, **Appendix Q** for 4-week (end of 4-week intervention period) survey items, and **Appendix R** for 2-week (post intervention period) follow-up survey items. Additionally, a subset of patients (up to 10) will be invited for a qualitative interview focused on study burden, facilitators/barriers to app use, satisfaction, and perceived utility in order to guide future refinements to the app (see Appendix T) when they complete use of the app at 4 weeks (end of intervention study period).

Intervention

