After the patient completes the baseline survey, the RA will meet with the patient (in person or virtually), to assist in either 1) downloading the application onto participants' mobile device or 2) providing/mailing the study phone to the participant. The RA will help to register the patient to the app and help set up any preferences. The RA will then conduct a 15-minute tutorial on the STAMP+CBT app and its intended use (Appendix S). The RA will also input the patient's pain medications from Epic, reconciling this list with the patient, and with the nurse navigator on the patient's care team if there are any discrepancies. As the nurse navigator is already a member of the care team, they'll have access to all Epic records and any documentation for this study included in Epic. The participant will also input their desired goal to work towards for the duration of the trial. During the trial, there is also a function in the app that allows participants to notify the research team if a medication or goal needs to be changed and reflected in the app. Final iterations to the app, research portal, and study procedures will be made following the initial few patients (up to 5) recruited to using the application. Thereafter, we will begin recruiting patients (up to 10) for the pilot study cohort.

Participants will utilize STAMP+CBT for 4-weeks (intervention study period). The 4 weeks will consist of all content introductions. Patients will also be offered the opportunity to continue their app use for the next 2 weeks (post-intervention period) until study completion (2 week follow up and survey), this will allow us to assess feasibility and acceptability of the appropriate length of use for the intervention. STAMP+CBT hosts and organizes patients' opioid/non-opioid analgesics. It has an extensive multi-media library of education content related to pain management (Appendix C)

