and pain specific CBT concepts (Appendices C, D, and F). Content will be delivered on a schedule to ensure that patients receive all pain CBT and medication education available (Appendix U). STAMP+CBT prompts patients to take daily surveys for reporting of pain, pain catastrophizing, mood, opioid/pain medication use, and sleep symptoms and progress towards individualized goals (Appendix U). At the end of each survey, patients receive feedback according to their symptom severity, with links to tailored educational content about pain and psychological symptom management. (Appendix U). Patients also complete weekly surveys for reporting symptoms listed above as well as goal progress. If patients report any severe symptoms, they are instructed to contact their care team immediately, with a telephone number included on the application screen, see table 2, or to go the Emergency room/call 911 for a true medical emergency. If patients' pain is poorly controlled but not severe enough to be prompted to immediately contact their care team (for example if their average pain is above a 4 and not acceptable), they are reminded to contact their care teams if their symptoms worsen or they are concerned about it.

One protocol-mandated study staff outreach to patients will occur within a week of enrollment. An RA will call to assess any technical or usability problems with the app (e.g. how to access the app on their phone, where to find certain study areas, etc.). These technical discussions will be optional for the patient and more can be scheduled if requested. Thereafter, the RA will monitor the STAMP+CBT dashboard twice daily (Mon-Fri), for any patient reported severe symptoms (Table 2). If a patient reports one of these severe symptoms, the RA will contact the patient's nurse through a secure EPIC message to notify the patient's care team. Additionally, to assist in population management, a *tiered system notifications*, in the portal will indicate symptom severity, need for outreach and/or management changes (See Table 3). As an additional safety measure, the application always prompts the patients to contact their care team for any severe symptoms they report and there is no expectation for proactive clinician outreach. These procedures have been approved by participating clinic nurses. The application provides a direct link to call the Outpatient Palliative Care Clinic at DFCI.

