- 11.2 Statistical analyses will be utilized in the pilot intervention portion of this study to ascertain feasibility and acceptability. We will measure time spent on the app per day and per week, completion rates for surveys and content review, and frequency of log-ons over the course of the pilot. The primary objective is to determine feasibility and acceptability of STAMP+CBT. Defined using precision analysis, we will consider the intervention to be feasible if >70% of subjects complete \geq 4 of the 6 pain-CBT modules and patients will complete 50% of surveys by the end of 4-weeks (completion of the 4-week intervention study period and completion of the 2-week post intervention period).^{40,41} A module will be considered complete if the participant engages in >70% of its content, including completing mHealth survey items, psycho-educational content, and app exercises. The intervention will be considered acceptable if >80% of the acceptability items are rated 4 or higher/5; lower ratings will lead to app refinements. Other feasibility measures will assess time to accrual, participation rates, and study retention and completion rates. Power calculation: With 10 patients, we will be able to estimate these proportions with margins of error (half of a 95% confidence

interval) of approximately 18% or less assuming that the feasibility threshold of 70% is reached. This margin of error is small enough so that proportion estimates relevant to study feasibility will be accurate and provide informative guidance for future, larger studies. Although power is not sufficient in this pilot, we will explore associations between levels of engagement and changes in pain severity/interference, opioid use, catastrophizing, sleep, mood, and pain self-efficacy.

- 11.3 The data the research team will access regarding app utilization will include; date and time of app log-ins, date of time of survey completion, survey responses, including clinical reporting of daily symptoms and medication usage, total app log-ins during intervention period, percent of surveys completed during intervention period, date time and frequency patients access external educational content.
- 11.4 PHI data will be collected using REDCap and the STAMP+CBT app.

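### The week-4 acceptability ratings may be given by phone or Zoom to an RA, a role that also onboards and supports patients; this may bias them upwards, and the plan neither limits nor records it

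*Combined protocol and SAP*

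**What the plan says.** **Instrument.** Section 9.3 (Survey assessments) places the acceptability scale in the survey at the end of the 4-week intervention: "patients will rate their satisfaction with STAMP+CBT using the 6-item Acceptability E-scale".

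**Modes.** The same section lets the survey be completed through a REDCap link, "over the phone with the RA, over Zoom with the RA", or "in person with pen and paper or on a tablet". No mode is fixed for the acceptability items.

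**Decision rule.** Section 11.2 calls the intervention acceptable "if >80% of the acceptability items are rated 4 or higher/5". Section 8.1 states the same rule and adds what follows from a poor result: "of the acceptability items are rated 4 or higher/5; lower ratings will lead to app refinements".

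**RA role.** Under Intervention in Section 9.3, the RA helps to install and register the app and enters the medications. Then: "The RA will then conduct a 15-minute tutorial on the STAMP+CBT app and its intended use". Within a week of enrollment, "An RA will call to assess any technical or usability problems with the app"; after that the RA monitors the dashboard twice daily on weekdays. Section 9.2 adds that "the RA will contact participants after 4 weeks (end of intervention period), and 6 weeks", to schedule the interview and confirm that surveys are complete.

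**Safeguards.** The main text does not ask for self-completion of the acceptability items, for a different RA to collect them, or for the mode to be recorded or used in the analysis.

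**The concern.** A satisfaction rating given to someone who helped deliver the service is open to courtesy bias, and the expected direction is upwards. The trial has a single arm, so no comparator would share such a shift and cancel it; it would go straight into the share compared with 80%. Acceptability is part of the primary objective, and about ten patients supply the ratings. A few ratings lifted from 3 to 4 can change the result, and low ratings are meant to prompt changes to the app. Because the mode is not recorded, nobody could later tell whether this had happened.

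**Working it through.** The plan gives no figure for a mode effect, so there is none to reproduce. Its one computed figure, a margin of about 18 points with 10 patients, is not used here. What follows shows how sensitive the rule is to an assumed shift; it does not estimate the bias.

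**Inputs from the plan**
- Analysis set: up to 10 patients (Section 9.3, Pilot Cohort); 10 are used here.
- Items: 6 (Section 9.3, Survey assessments).
- Rule: more than 80% of items rated 4 or 5 (Sections 8.1 and 11.2).

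**Assumptions, not in the plan**
- Counting: ratings are pooled over patients and items. The plan does not define the unit.
- True favourable share: p = 0.75.
- Within-patient correlation: ρ = 0.2 or 0.4.
- Mode effect: 5 or 10 points on p for an RA-read patient.
- Exposure: 3 of 10 patients RA-read, with 10 of 10 as the extreme.

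**Step 1: pass mark.** There are 10 × 6 = 60 ratings and 0.80 × 60 = 48. The rule says more than 80%, so a pass needs at least 49. From 45 of 60 (75%), 49 − 45 = 4 lifted ratings are enough. From 48 of 60 (80%), one is enough.

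**Step 2: average shift.** With 3 of 10 exposed, the average share is 0.75 + 0.3 × 0.05 = 0.765 or 0.75 + 0.3 × 0.10 = 0.78. In ratings, 18 × 0.05 = 0.9 or 18 × 0.10 = 1.8 extra favourable answers are expected.

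**Step 3: chance of passing.** Each patient's favourable count is beta-binomial with 6 trials, a = p(1/ρ − 1) and b = (1 − p)(1/ρ − 1). At p = 0.75 this gives a = 3, b = 1 for ρ = 0.2, and a = 1.125, b = 0.375 for ρ = 0.4. Adding ten independent patients exactly (by convolution) gives P(total ≥ 49):

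| RA-read patients | Gain | ρ = 0.2 | ρ = 0.4 |
|---|---|---|---|
| 0 of 10 | none | 0.239 | 0.290 |
| 3 of 10 | 5 points | 0.302 | 0.345 |
| 3 of 10 | 10 points | 0.373 | 0.404 |
| 10 of 10 | 5 points | 0.480 | 0.493 |
| 10 of 10 | 10 points | 0.752 | 0.719 |

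What drives the result is mainly the average shift over all patients. Five of 10 exposed with a 10-point gain (average 0.80) gives 0.479 and 0.492, almost the same as all 10 gaining 5 points.

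**Step 4: dependence on the baseline.** A true share of 75% lies close to the cut, where the rule is sensitive. At a true share of 90% with no mode effect, the chance of passing is already 0.938 (ρ = 0.2) or 0.901 (ρ = 0.4), so a shift can change little.

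**The case against.** The case on the other side is substantial.

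- **Same person.** A reader might infer that the RA who trained a patient also takes that patient's ratings. The text does not say so. It alternates between the definite and indefinite article, and Section 23.1 speaks of research assistants in the plural. It does not rule this out either. With a different RA, the patient would still be rating the team's app to a member of the team.
- **Proven inflation.** A reader might infer that scores will be pushed up. The documents give no information on mode effects. The direction is an ordinary methodological expectation, and the size is unknown.
- **Exposure.** RA-assisted completion is one option among several, and the REDCap link is listed first. Section 23.1 describes private, remote completion and lets patients skip questions. Section 9.2 has the RA confirm completion at week 4, not read items out. A Zoom session could use screen sharing without spoken ratings. Exposure may therefore be small or nil. None of this withdraws the phone and Zoom options.
- **Other evidence.** Section 8.2 combines qualitative and quantitative results. Exit interviews also guide refinements, and Section 11.2 adds app-usage data. So it would be too strong to say that the signals for refining the app are suppressed. The 80% rule still rests on the ratings alone.
- **Flexible modes.** These are reasonable for ill patients. Mixed modes do not undermine a planned comparison, because no between-patient comparison of acceptability scores is planned.
- **Appendices.** Appendices I, Q and S were not available and may specify how the items are given.

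**Conclusion.** The point holds as an avoidable risk of upward bias in a decision rule for the primary objective, not as a demonstrated bias. The main text permits the acceptability ratings to be given to an RA, assigns onboarding and support to the same role, and neither limits nor records the mode.

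On the assumptions above, 3 of 10 patients RA-read with a gain of 5 or 10 points moves the chance of passing from about 24–29% to about 30–35% or 37–40%. The larger values, about 48–49% and 72–75%, apply only if the average favourable share over all patients rises by 5 or 10 points. They should not be read as the expected effect. All these figures depend on pooled counting, a true share near the cut, and an assumed mode effect. They also take the acceptability items in the rule to be the six E-scale items.

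The usability scale (SUS) has no pass threshold, so this argument does not reach it. I would rate the point as a cheap improvement.

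**What to change.** In Section 9.3, Survey assessments:

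1. Make self-completion (REDCap link, tablet or paper) the default for the six E-scale items at week 4, completed before the exit interview.
2. Allow an RA to read the items only when the patient cannot self-complete, preferably an RA who did not onboard that patient, if one is available.
3. Record the mode for each patient.

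In Section 11.2, report how many ratings were RA-read and give the acceptability result without them. With about 10 patients this is descriptive only.

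Other survey sections can keep every mode. Applying the same default to the SUS is optional. If Appendix I, Q or S already sets the mode, a cross-reference would be enough for that part.

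The cost is a sentence or two and one mode field; the self-completion routes already exist. The downside is that a few unwell patients may leave items blank, which the RA-read fallback is there to cover.

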1.0 Objectives*

- As a pain psychologist and palliative care researcher, I developed 1. develop a novel mHealth intervention that harmonizes psychological and pharmacological support for advanced cancer pain. I adapted core components of pain-CBT and integrated them into STAMP (Smartphone Technology to Alleviate Malignant Pain), an existing NINR-funded cancer pain mHealth intervention. STAMP enables patients with advanced cancer to track their pain, opioid use, and side effects. It delivers tailored education and self-management advice while facilitating clinician monitoring and patients' proactive outreach. Having developed an extensive suite of multi-media cancer pain psycho-education covering core pain psychology principles, I seized a strategic opportunity to refine and integrate pain-CBT treatment into medically oriented self-management support in STAMP. Capitalizing on mHealth technology, I strove to destignatize pain psychology through a potentially scalable model that can disseminate behavioral treatments for advanced cancer pain paired with their palliative care pain management plan. My aim is to:
 - Determine feasibility and acceptability of the STAMP+CBT app: up to 15 patients with advanced cancer pain will be recruited from outpatient palliative care clinics at a major cancer center to participate in a single-arm, 6week study of STAMP+CBT (4-week intervention period and a 2-week post intervention period). Surveys at baseline, 4 weeks (end of intervention period), and 6 weeks (end of 2-week post intervention period) will explore trends in pain specific intensity, self-efficacy, and catastrophizing, physical function, opioid use, and quality of life. End-ofstudy interviews will identify facilitators and barriers to usability, acceptability, and satisfaction of the app. The primary outcome will be feasibility evaluating 1) app retention rates and 2) completion of app exercises.

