Participants will include DFCI patients presenting to outpatient palliative care, GCC, or satellite (MV and LD) clinics with ongoing chronic cancer pain management issues. Participants will meet with the study team in person, over the phone, or via a compliant and secure video chat/screen- share platform (i.e. Zoom). We will conduct the pilot cohort with up to 15 patients. Each participant will receive a \$25 gift card upon completion of the 4-week intervention period, and another \$25 gift card upon completion of the 2-week post intervention survey. The first 5 patients will onboard to the application and their involvement/feedback will focus on making final revisions onboarding for the application and study procedures. Therefore, the following 10 patients' data will be included for pilot study analysis and feasibility findings.	 Use the STAMP+CBT mobile app for 4 weeks (intervention period, 4 weeks for content introduction, extended 2 weeks for review of content if patient's request this) Engage with pain CBT content including a goal-setting module, relaxation exercises, and educational content Daily and weekly reporting of pain, catastrophizing, mood, and sleep symptoms and painkiller usage and satisfaction through the app (Appendix U) Complete survey assessments at baseline, 4 weeks (end of intervention period), and 6 weeks (end of 2-week post intervention period) assessing pain severity, self-efficacy and catastrophizing, physical function, opioid use, and quality of life outcomes. (Appendices P, Q, R) End-of-intervention interview (4 weeks) assessing usability and acceptability (Appendix T)
	• Wedical Record Abstraction (Appendix O)

 Table 1. Brief description of pilot cohort activities

PILOT COHORT:

The first few patients (up to 5) will onboard to the application and their involvement/feedback will focus on making final revisions to the mobile application and study procedures. All procedures will be the same for the 15 patients, however, data for the initial patients (up to 5) will not be included in final analysis as their involvement will be focused on revising final app bugs/iterations and modifications to study procedures before the pilot trial initiation. The following patients (up to 10) will be considered as the core pilot study participants to evaluate feasibility and acceptability of the application and study procedures.

Survey assessments

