To minimize the burden of the intervention on clinicians, there are no automated clinician alerts (i.e. email or in-basket message) for severe symptoms, rather, patients are prompted to call their care teams or 911 (emergency services) if they report severe symptoms (Table 2 and 3). Patients are reminded frequently throughout the application that the research portal is not monitored around the clock and therefore they should reach out for urgent needs. Reports (with summarized pain and psychological symptoms; opioid use data; side effects; patients' goals and reported goal attainment) will be sent to nurse managers, palliative care providers, and

oncologists to enable effective communication, opioid titration, and other management changes when prompted by the patient.

During the study patients will be asked to complete 3 survey assessments, one at baseline, one at the end of the 4-week intervention period, and another at the end of the 2-week post intervention period. Patients will also be invited to complete a short semi-structured interview about their experiences using the application (See Appendix T). See below for description of the surveys (Table 5).

Pain	• Worst pain = 9-10
	• Worst pain = 7-10 and new pain
Red Flag	Severe weakness or fatigue
Symptoms	• Lightheadedness or feeling like I was going to pass out
	• No gas or stool from my bottom (or ostomy) in the last
	2 days
	• Vomiting 2 or more times in the last 24 hours
	• Fever of 100.5 or greater
	• New or worsening chest pain
	• New or worsening shortness of breath
	New or worsening back pain
	• New numbness and weakness in one or both of your
	legs
	• Severe difficulty eating or drinking
	Hallucinations/nightmares
Opioid Side	Hallucinations
Effects	

Table 2. Severe Symptoms

Relief with opioids	No relief
	OK
	Unsure
	Good relief
Pain Control	Poor
	Suboptimal
	Good
Other Severe Symptoms	Number of severe symptoms on Table 2
	shown in red
Opioids need updating	Yes
	No
Mood	IF Patient responds to mood questions 17-
	20 with a total score of ≥ 12 : Low Mood
	IF Patient responds to mood questions 17-
	20 with a total score of <12: High Mood
Catastrophizing	IF Patient responses to catastrophizing
	questions 12-16 with a total score greater
	than ≥ 10 : High Stress
	IF Patient answers catastrophizing items
	12-16 with a total score <10: Low Stress
Sleep	If sleep item 23 on the survey score ≥ 3 :
	Poor
	If score <3: Good
Goals need updating	IF Patient answers "No, it needs to be

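### The barriers interview is tied to week 4, so patients who never onboard or who withdraw earlier have no stated route to it

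*Combined protocol and SAP*

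**What the plan says.** **Purpose.** Section 1.0 says that "interviews will identify facilitators and barriers to usability, acceptability, and satisfaction of the app". Section 8.1 puts the same material inside Endpoint 1: "we will explore barriers/facilitators, suggested changes to content, acceptability of intervention engagement, and whether app use continues after completion". Sections 8.2 and 11.1 then use the results to revise the app and the study procedures before a larger efficacy study.

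**Who and when.** The Survey assessments paragraph of Section 9.3 is the fullest statement: "a subset of patients (up to 10) will be invited for a qualitative interview focused on study burden, facilitators/barriers to app use, satisfaction", with the invitation made "when they complete use of the app at 4 weeks (end of intervention study period". Table 1 lists an "End-of-intervention interview (4 weeks) assessing usability and acceptability" among the components of participation. Section 9.2 states that "the RA will contact participants after 4 weeks (end of intervention period), and 6 weeks (end of 2-week post-intervention period", and adds: "The purpose of these contacts would be to schedule the end of intervention interview and confirm completion of survey assessments". The Intervention part of Section 9.3 is broader: "Patients will also be invited to complete a short semi-structured interview about their experiences using the application".

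**Early exits.** Section 13.1 withdraws patients who have not completed onboarding within 3 weeks of enrollment. Section 13.2 has staff inform them. Neither mentions an interview or a record of the patient's reasons.

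**The concern.** Patients who never start, or who give up in the first weeks, are likely to know most about what stands in the way of using the app. An interview that opens at week 4 hears mainly from those who got that far. Its themes would then describe what helps people use the app better than what stops them.

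That selection matters because the themes are the plan's main source of reasons, and they feed directly into redesign. If early leavers are missing, burden, illness or difficulty in starting could be under-reported, and the efficacy study could inherit the same losses. The primary feasibility proportion is not affected. What is at stake is the explanation that goes with it.

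**Working it through.** The plan gives no figure on this point to reproduce. The check is a comparison of the text, followed by an illustration of scale.

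**Step 1. The interview statements side by side.**

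| Place | Who | When | Completed use required? |
|---|---|---|---|
| 9.2 | Participants contacted by the research assistant | After 4 weeks | No |
| 9.3, Table 1 | Pilot cohort patients | 4 weeks | No |
| 9.3, Survey assessments | Subset, up to 10 | On completing use at 4 weeks | Yes, if read literally |
| 9.3, Intervention | Patients | Not stated | No |

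Section 1.0 calls them end-of-study interviews, which is no earlier than week 4 either.

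**Step 2. Apply these to three kinds of early stopper.**

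- *Never onboarded.* Withdrawn at 3 weeks under 13.1, before the week-4 contact. No supplied statement provides an interview.
- *Withdrew before week 4.* No supplied statement provides an interview.
- *Stopped using the app but stayed enrolled.* Reached under 9.2, Table 1 and the Intervention text. Left out only if the Survey assessments wording is taken as a condition and not as a time point.

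**Step 3. Could other data supply the reasons?**

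- The research assistant's call within a week of enrollment (9.3, Intervention) is optional for the patient and covers technical or usability problems. Further calls depend on a request.
- App data (11.2, 11.3) record log-ins, time on the app, survey completion and content access. They show when use stopped, not why.
- In Table 5, the satisfaction and usability measures are collected only at T2, which is week 4.

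**Step 4. Scale.** Inputs: n = 10 core patients (9.3). The early-stopping share d is not in the documents, so d = 10% to 30% is assumed, with patients independent of one another.

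Expected number = n × d. P(at least one) = 1 − (1 − d)^n.

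| d | Expected of 10 | P(at least one) |
|---|---|---|
| 10% | 10 × 0.10 = 1 | 1 − 0.90^10 = 0.65 |
| 20% | 10 × 0.20 = 2 | 1 − 0.80^10 = 0.89 |
| 30% | 10 × 0.30 = 3 | 1 − 0.70^10 = 0.97 |

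These counts cover early stoppers of all three kinds. All are missed on the literal reading; on the broader reading, only those who have left the study are.

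**Step 5. The limit of 10.** Ten interviews can cover all 10 core patients. But Section 9.3 applies the same procedures to all 15 patients, including up to 5 run-in patients. If run-in patients are interviewed too, up to 15 − 10 = 5 patients go without, and no selection rule is given.

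**The case against.** The strongest reply is that the interview is less restricted than it first looks. Three of the four statements in Step 1 set no completion condition, and the fourth can be read as naming a date. This stands. A reader might infer that everyone who stops early goes unasked, but the documents do not support that for patients who stay enrolled.

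A reader might also try to size the gap from the feasibility rule. More than 70% of 10 means at least 8, so the rule fails with 3 or more patients short of the criterion and passes with up to 2. Those counts do not measure missed interviews. The criterion concerns modules and surveys. A patient who completes too few modules but is still enrolled at week 4 falls short of it and is still contacted under Section 9.2.

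Nor would the trial be unable to explain a failure at all. The week-1 call, the app logs, the chart abstraction of deaths and health care use, and the run-in patients' feedback on onboarding all contribute something. They do not replace asking leavers for their reasons.

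Finally, Appendices S (onboarding and monitoring), T (interview guide), X (study letter) and AD (consent form) are not in the supplied text. Section 13.3 refers to partial withdrawal, so some procedures may continue for some withdrawn patients. This limits the finding to what the supplied text provides. Some early leavers will also be too ill to interview, or will have died, whatever the plan says.

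**Conclusion.** The point holds for two groups: patients withdrawn for not onboarding, and patients who withdraw before week 4. Nothing supplied gives either group an interview or asks for their reasons. For patients who stop use but remain enrolled, the fault is inconsistent wording about who is invited, not a clear exclusion.

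The likely effect is that barrier themes under-represent early leavers. Its size cannot be taken from the documents. Under the assumed 10% to 30%, it concerns about 1 to 3 of 10 core patients, and fewer if some of them stay enrolled and are reached at week 4. The component is exploratory and the pilot small, so this is an inexpensive improvement and not a threat to the primary estimate. It rests on the supplied text; the missing appendices could narrow it.

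**What to change.** Reconcile Section 9.2, Table 1, and the Survey assessments and Intervention parts of Section 9.3 so that they all say the following:

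- All core patients will be invited to interview at 4 weeks or, if it comes first and they agree, soon after they stop using the app, withdraw, or are withdrawn under Section 13.1. The team should fix the time window and define stopping from the log-in data already collected under Section 11.3.
- Within the limit of 10 interviews, core patients come before run-in patients, and early stoppers come first among core patients.
- Patients who never onboarded are asked only about their reasons for not starting and about study burden, since they have no experience of the app to describe.

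When themes are reported, state how many contributing patients did and did not meet the feasibility criterion. Separate analyses are not needed, since one group may hold only a few patients.

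**Cost.** Wording in the places named above, with minor changes to the consent form and interview guide. Some interviews will take place earlier, and some early leavers will decline or be too ill. No staff or sample size is added, and staff already contact patients withdrawn under Section 13.1, so there is a natural moment to ask.
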